4.6.1 Early Termination Study Visit

During any of the visits, if any subject decides to withdraw prior to completion of all study materials, the research team will review the individual circumstances and decide whether any data already collected will be included in further analyses. These decisions will be based on whether enough data has been collected to adequately complete our planned analysis. If at any time any subject requests to have information they have submitted withdrawn from consideration, we will abide by their request and remove that data from our research database.

5 STUDY EVALUATIONS AND MEASUREMENTS

5.1 Screening and Monitoring Evaluations and Measurements

5.1.1 Evaluations, Measures

Measures for Co-Design

- Follow-Up focus group (See Appendix 11.5 for focus group guide)
- Post-focus group survey (See Appendix 11.6 for survey)
 - *Demographics of co-design participants*: The following baseline data will be collected: role in the co-design, gender, race, and ethnicity.
 - *Perception of co-design process and level of engagement*: Modified version of “Coalition Effectiveness Inventory”¹¹⁰⁻¹¹² that consists of one 14-item section measuring participants’ perceptions of the Co-design leader’s effectiveness and one 10-item section measuring participants’ perceptions of their own involvement and commitment to the Co-design process.

Measures for Post-Intervention

- *Course Evaluation - Satisfaction with CST and perception of skill usefulness*: This course evaluation is designed to determine clinicians’ perception of usefulness and satisfaction with the CST program. They will be asked to rate their level of agreement with aspects of the course on a 5 point Likert-type scale. Furthermore, the current burnout rate of clinicians will be assessed using the Maslach burnout score.¹⁰³ Additionally, changes that CICU clinicians have implemented regarding family meetings due to the 2020 COVID-19 pandemic will be recorded. Finally, clinician demographics will be collected including role in CICU, gender, race, and ethnicity. See Appendix 11.11 for complete course evaluation, Maslach burnout score, and COVID Change in Practice survey
- *Intervention fidelity checklist*: The Fidelity Checklist is a list of 7 behaviors of clinicians used to determine if clinicians used the tools and documents taught in the intervention. See Appendix 11.12 for the Intervention Fidelity Checklist
- *Acceptability Interview - 1 month follow-up*: We will do a semi-structured interview with clinicians reviewing their experience of the intervention process including what worked well and what they would recommend changing. Emphasis will be placed on virtual aspects of the training given the novelty of the implementation due to the COVID-19 pandemic. The semi-structured interview guide is in Appendix 11.13

Surveys for Clinicians Participating in Actual Family Meetings

- *Demographics of clinician participants*: The following data will be collected regarding clinician subjects: discipline, age, gender, ethnicity, race, number of years in practice, estimated number of family meetings conducted in a week, estimated average time spent on conducting family meetings, previous experience with communication skills training.

- *Team member perception and satisfaction with collaboration:* The Baggs CSACD-N tool^{94,109} will measure team member perception and satisfaction with collaboration both pre and post-CST. Clinicians will rate their level of agreement for 9 items on a 7-point Likert-type scale from “Strongly disagree” to “Strongly agree.” This tool will capture each discipline’s experience with collaboration with other team members and satisfaction with care decisions.

Survey Measures for Parent-patient Dyads

- *Demographics of parent-patient dyads:* The following baseline data will be collected regarding parent-patient dyads: age, gender, ethnicity, race, education level, and health literacy.
- *Parental preference for decision making control:* The Control Preferences Scale for Pediatrics (CPS-P)¹¹³ is a 5-item sorting measure of parent preferences for participation in treatment decision making.
- *Parental anxiety and depression:* The Hospital Anxiety and Depression Scale (HAD)¹¹⁴ is a 14-item measure of depression and anxiety.
- *Parental post-traumatic stress:* The Impact of Event Scale-Revised (IES-R)¹¹⁵ is a 22-item measure of post-traumatic stress disorder.
- *Parental trust in medical team:* The Trust in Physician Scale¹¹⁶ is a 10-item measure of trust in physicians.
- *Parental satisfaction with decision-making:* The Pediatric Family Satisfaction with Care in the Intensive Care Unit (PFS-ICU 24)¹¹⁷ is a 24-item tool and will measure (1) satisfaction with care and (2) satisfaction with medical decision-making, modified for parents/caregivers of critically ill children. The Communication Assessment Tool-Team (CAT-T)¹¹⁸ is a 15-item tool that will measure patient perception of communication with the medical team and is adapted to team environments. A more complete outline of the survey is described below in the Appendix 11.14.
- *Parental feelings about communication with the clinical team:* myICU¹¹⁹ is an 11 item tool adapted by the authors of the tool to assess a surrogate’s perceptions of how comfortable the surrogate feels discussing potential concerns they have with their child’s medical team regarding their child’s care in the ICU.
- *Parental involvement in other family meetings*
- *Fidelity of Parent Preparation and Acceptability:* Parents will be surveyed on whether they were given the Family Preparation Worksheet and whether clinicians followed up on how they used the worksheet. They will be asked what they thought of the worksheet. They will also be asked about their acceptability of the Family Meeting Summary Worksheet. The use and acceptability survey was adapted from a Shared Decision Making tool.¹²⁰ See Appendix 11.15 for specific items.
- *Medical record review:* Patient data will be retrieved from Epic and PC⁴ national database registry. Data listed below are main patient record variables. See Appendix 11.18 for full list of PC⁴ variables
 - Child’s name
 - Child’s MRN#

- Child's date of birth
- Child race/ethnicity
- Parent/legal guardian race
- Parent/legal guardian contact number
- Parent/legal guardian e-mail address
- Parent/legal guardian address
- Length of stay in the CICU
- Length of stay in the hospital
- EPIC Problem List
- Medication list and administration dates throughout hospitalization
- Limitations of interventions during study period
- Date of limitations of interventions during study period
- ICD-9 codes associated with hospitalization
- Date of discharge from CICU / Date of death/ discharge from hospital
- Discharge disposition from CICU and hospital (floor / home / rehab facility / palliative care / hospice)
- Palliative care consult
- Ethics consult
- Gestational age
- Fundamental Cardiac Diagnosis
- Chromosomal abnormalities
- Syndromes
- Cardiothoracic surgery and date
- Primary insurance type
- Discharge 30 day mortality status
- Number of prior cardiothoracic operations
- Reason for CICU encounter
- Non-cardiothoracic surgery
- Encounter cardiothoracic diagnosis
- Encounter medical diagnosis
- DNR/DNI on file
- Withdrawal of life sustaining therapy
- Bleeding requiring reoperation and date
- Unplanned reoperation/reintervention and date
- Sternum left open and date
- Cardiac arrest and date
- Stroke and date
- Risk group as measured by the STAT mortality category
- operative or post-operative complications

- Specialty notes related to CICU family meeting
- CICU Summary Worksheet

Interviews for Parent-patient Dyads in the Pre-Intervention

- The interviews will cover parents' experiences in family meetings and perspectives on communication with the clinical team. (See interview guide under Appendix 11.16)

Interviews for Parent-patient Dyads in the Post-Intervention

- The interviews will assess parents' acceptability of the parent-facing elements of the intervention, including preparing for the meeting and their perception of the written summary after the family meeting. (See interview guide under Appendix 11.17).

Quantitative Coding of Audio Recordings of Actual Family Meetings

- *Modified VitalTalk coding scheme named SCOPE*^{29,121,122}: The small number of new codes added will measure engagement by the attending physician or team members from other disciplines, and adherence to elements of best practices in family meetings (e.g., facilitating introductions of participants, setting an agenda, and summarizing what was discussed in the meeting). Coders will be trained in the coding scheme using a manual with detailed definitions of all the codes.
- *Medical Interaction Process System (MIPS)*⁸⁰: MIPS is a previously validated coding scheme with good psychometric properties that was developed for training clinicians in communication and related research⁸⁰. It has been used extensively in communication analysis^{83,123}. MIPS draws upon a patient-centered approach and codes individual utterances between providers and patients allowing for coding of both content and affective information.
- *Time each member speaks during meeting*: Team function will be analyzed by comparing the change in the number of minutes clinicians from each discipline speak in pre and post-CST meetings using linear regression and controlling for the length of the meetings.
- *Performance Assessment for Communication and Teamwork (PACT-Novice)*^{124,125}: The PACT Tool Set was developed to assess performance on team work and communication and builds upon the framework of TeamSTEPPS, a widely used system designed to improve patient safety, communication, and teamwork skills among health care professionals. The PACT-Novice tool will allow us to quickly train study staff to evaluate teamwork and communication behaviors.
- *Bruce et al. Evaluation Tool*¹²⁶: This novel evaluation tool was recently developed to assess family meetings, including clinician skills, team function, meeting leadership, and other elements of successful family meetings.

Clinician Schedule of Evaluations
--

Diagnostics/Measures	Co-design	Pre-CST Actual Meetings	Post-CST Evaluation	Post-CST Actual Meetings
Focus Group	X			
Focus Group Survey	X			
Course Evaluation including Maslach burnout score and COVID-19 questions, demographics.			X	
1 Month Follow-Up Acceptability Interview			X	
Demographics		X		X
CSADC-N		X		X
SCOPE		X		X
MIPS		X		X
PACT-Novice		X		X
Bruce et al. Evaluation Tool		X		X
Time each member speaks		X		X

Qualitative Coding of actual family meetings

- Using a grounded theory, audio recordings will also be coded by 2 coders for thematic content to better understand team functioning and collaboration
- Video recordings will be used for speaker attribution in the coding phase.

Qualitative Coding of parent-patient dyad interviews

- Using a grounded theory, audio recordings will also be coded by 2 coders for thematic content to better understand parental experiences communicating with the medical team in the CICU.

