3.1.5 Follow-Up Phase

Clinicians Participating in Intervention: After CST, a set of actual family meeting encounters with these trained clinicians will be audio recorded and coded, ensuring there are 23 meetings with each category of person trained. We estimate a total of 28 meetings will need to be recorded in order to obtain 23 meetings with each discipline. Clinicians participating in the intervention will complete an online survey after the actual family meeting that they are observed participating in.

This survey will measure team member perception and satisfaction with collaboration. We will administer the modified Baggs CSACD-N tool to all clinician team members who participate in an actual encounter, which will capture each discipline's experience with collaboration with other team members and satisfaction with care decisions.

Clinicians Not Participating in Intervention: Consented non-participating clinicians will have their normal, scheduled family meetings. Actual family meeting encounters with these clinicians will be audio or video recorded and coded. Clinicians not participating in the intervention will complete the same online survey as those clinicians participating in the intervention after the observed actual family meeting.

Parent-patient Dyads Participating in the Survey or Interview After Intervention: Potential subjects will be screened using the protocol inclusion and exclusion criteria. Parent-patient dyads will be recruited into the study in person, over the phone, or via e-mail. The goal for enrollment will be up to 50 parent-patient dyads, with 30 evaluable parent-

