4.5.1 Clinicians Participating in Intervention: Visit 5-30

- Clinician audio recorded during actual family meeting
- Administration of follow-up online survey about clinicians' perception of team function in person or via email

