Team function will be analyzed for simulated family meetings by comparing the change in the number of minutes that clinicians from each discipline speak in pre and post-CST meetings using linear regression and controlling for the length of the meetings.

To assess the impact of the CST program in actual family meetings, audio recordings from actual family meetings will be coded and compared to coded audio recordings from pre-intervention actual family meetings. Since there are generally at least 2 clinicians in each team encounter, we will examine the individual skill acquisition within each part of the team encounter. Within each discipline, there are several clinicians involved in multiple team meetings. We will use fixed-effects regression with a clinician identifier variable as a covariate so that we can examine the effect of CST intervention on skill acquisition, adjusting for the effects of individual clinicians.

Team function will be analyzed in the same way as in simulated meetings by comparing the change in the number of minutes that clinicians from each discipline speak in pre and post-CST meetings using linear regression and controlling for the length of the meetings.

The difference in team member perception and satisfaction with collaboration will be measured after their participation in clinical encounters both pre and post-CST by administering the modified Baggs CSACD-N tool to all clinician team members who participate in an actual encounter. This tool will capture each discipline's experience with collaboration with other team members and satisfaction with care decisions. Means and standard deviations will be calculated for the tool and t-tests will determine if there are significant differences for each discipline pre and post-CST.

Hypotheses will be tested using logistic regression modeling with significance of the two-tailed hypothesis tests set at alpha equal to 0.05.

Clinician perception of the usefulness of CST and satisfaction with the training will be identified by descriptive statistics and differences in the mean and median scores will be calculated to determine retention in perceptions of usefulness one month after the training.

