6.4 Sample Size and Power

We hypothesize that the CST will change clinician behavior by increasing the number of skills demonstrated in a simulated family meeting. Sample size calculations using existing data about acquisition of skills being evaluated in the CST²⁹ demonstrated that a total of 20

clinicians will be needed to identify significant changes in the following skill outcomes: discussing the big picture, responding to emotion, and performing several empathetic verbal skills using 80% power and an alpha=0.05.

Sample size calculations for determining change in clinician skill acquisition by discipline requires that there be an adequate number of actual encounters recorded such that they can be analyzed by provider type. Sample size calculations for simulated family meetings apply here as well in that we will need to have at least 20 team encounters pre and post-CST intervention to be able to look at the change in outcome before and after the intervention. Since there are generally at least 2 clinicians in each team encounter, we will examine the individual skill acquisition within each part of the team encounter. Within each discipline, there are several clinicians involved in multiple team meetings. We will use fixed-effects regression with a clinician identifier variable as a covariate so that we can examine the effect of CST intervention on skill acquisition, adjusting for the effects of individual clinicians.

Team function will be analyzed by comparing the change in the number of minutes that clinicians from each discipline speak in pre and post-CST meetings using linear regression and controlling for the length of the meetings. Sample size calculations based on previous data⁸⁷ and assuming 80% power and an alpha=0.05 will only require 3 paired respondents pre and post-CST to identify significant differences.

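### The speaking-time regression has no clinician term, so its 5% error rate fails when the clinicians observed differ between phases

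*Protocol*

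**What the plan says.** Protocol sections 5.1.1, 5.2.1, 6.2, 6.3.2 and 6.4 all describe the same team-function analysis. Section 5.1.1 compares the "number of minutes clinicians from each discipline speak in pre and post-CST meetings using linear regression and controlling for the length of the meetings". For actual meetings, section 6.3.2 adds only this: "Team function will be analyzed in the same way as in simulated meetings". Phase and meeting length are the only terms named.

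The same section treats skill acquisition differently. It observes: "Within each discipline, there are several clinicians involved in multiple team meetings". For that outcome it then says: "We will use fixed-effects regression with a clinician identifier variable as a covariate". Section 6.4 repeats the contrast.

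On who is observed:
- Section 3.1.3 describes pre-CST recording of clinicians outside the intervention only.
- Section 4.3 says the clinicians due to be trained are assessed in actual encounters before training.
- Section 3.1.5, on post-CST meetings with trained clinicians, says: "We estimate a total of 28 meetings will need to be recorded in order to obtain 23 meetings with each discipline".
- Section 3.3.2 expects at least 20 trainees and about 300 non-participating clinicians.

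The SAP (Aim 2c) models words spoken by physicians versus parents, adjusted for meeting length. It then allows mixed models that account for repeated measurements within participants, on condition that sample size allows and the univariate associations are significant.

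**The concern.** People differ in how much they talk. If a discipline is represented by one set of clinicians before training and a different or smaller set afterwards, part of the pre/post difference in minutes reflects who was in the room. A regression that treats every meeting as independent counts repeated meetings with one person as fresh evidence, and its standard error does not include the variation between clinicians.

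The number present matters as well. The text does not say whether minutes are totalled over a discipline's attendees. If they are, a second attendee can look like a change in collaboration.

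At stake is whether a significant result for a discipline can be read as a change in team function at the stated 0.05. The authors saw the dependence and dealt with it for one outcome from these recordings but not for this one.

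**Working it through.** **The plan's own figure.** Section 6.4 says 3 paired respondents suffice, "assuming 80% power and an alpha=0.05". Section 6.3.2 makes tests two-sided: "significance of the two-tailed hypothesis tests set at alpha equal to 0.05". No difference, SD or correlation is given, so the figure cannot be reproduced. Solving backwards, P(T > 4.303) = 0.80 for a noncentral t with 2 df and noncentrality d√3 gives d = 3.26 SDs of the paired difference. The normal approximation gives (1.960 + 0.842)/√3 = 1.62. Either way it says nothing about clinician correlation, and it assumes pairs that the regression does not model.

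**Inputs.**
- From the protocol: 23 post-CST meetings per discipline (3.1.5).
- Assumed: 23 pre-CST meetings as well; one clinician of the discipline per meeting; the clinician numbers and overlap shown below; within-clinician correlation ρ of 0.1, 0.3 and 0.5.
- The SAP speaks of 230 meetings per phase. I use 23 because the per-discipline analysis is the protocol's. More meetings from the same people would widen the gap, because the clinician part of the variance hardly shrinks.

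**Formula.** Set the variance of minutes, given length, to 1, with a share ρ between clinicians. Let w be each clinician's share of a phase's meetings.
- True variance of the phase difference = ρ·Σ(w_pre − w_post)² + (1 − ρ)·2/23.
- With K clinicians attending at random, the expected Σw² in a phase is 1/K + (1 − 1/K)/23. This is 0.163 for K = 8, 0.362 for K = 3 and 0.283 for K = 4.
- Variance the model reports ≈ [(1 − ρ) + ρ·(23/22)·(1 − mean Σw²)]·2/23.

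**Worked at ρ = 0.3.**
- 8 pre, 3 post, none shared. Clinician term: 0.163 + 0.362 = 0.525. True variance: 0.3 × 0.525 + 0.7 × 2/23 = 0.158 + 0.061 = 0.218. Reported: (0.7 + 0.231) × 2/23 = 0.081. True SE / reported SE = √2.70 = 1.64.
- The 3 are among the 8. Clinician term: 0.525 − 2 × 3 × (1/8)(1/3) = 0.275. True variance: 0.083 + 0.061 = 0.144. Ratio √1.77 = 1.33.
- The same 4 in both phases, attending at random. Clinician term: 0.565 − 0.500 = 0.065. True variance: 0.020 + 0.061 = 0.080. Reported: 0.080. Ratio 1.00.

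**False-positive rate of the planned regression** (simulation, no true phase effect, minutes on phase and length, 20,000 runs per cell):

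| Clinicians of the discipline | ρ = 0.1 | ρ = 0.3 | ρ = 0.5 |
|---|---|---|---|
| 8 pre, 3 post, none shared | 11% | 22% | 32% |
| 8 pre, 3 post, the 3 among the 8 | 8% | 13% | 19% |
| Same 4 in both phases, attending at random | 5% | 5% | 5% |

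Shorter runs with other seeds move the first two rows by about one point (11/23/31% and 7/12/18%). The simulated SE ratios at ρ = 0.3 are 1.64, 1.34 and 1.01, in line with the formula.

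If the same 4 clinicians each attend 6 meetings per phase (3,000 runs), the rate is 4.2%, 3.3% and 1.9%. The reported SE is then too large.

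**The case against.** **The error bars may not be too narrow.** This stands as a limit on the point. With the same clinicians in both phases the test holds its level, and with balanced attendance it is conservative. Section 4.3 and the mention of pairs in section 6.4 suggest overlap. Section 3.1.3 suggests none, and the schedule of study procedures lists no pre-CST meeting for intervention clinicians. Nobody can rely on overlap until these passages are reconciled.

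**The SAP already accounts for repeated participants.** Partly true. It has a mixed model, an optional count of participants at the meeting, and a floor of five participants for stratifying by physician type. But the mixed model runs only after the unadjusted test is significant, so it cannot repair that test. It is not clearly applied to speaking time, which is listed among its covariates. The SAP's speaking-time outcome is words by physicians versus parents, not minutes per discipline, and its count is not per discipline.

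**A reader might infer that one to three people supply each discipline's data**, from 20 trainees over six named groups and the heading "Clinicians Participating in Intervention: Visit 5-30". The documents do not support this. Twenty is a minimum, the visit range is not an expected load, and untrained clinicians are also recorded after CST.

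**A reader might also infer a known attendance bias**, from 23 of 28 meetings (82%) after training. No pre-CST attendance rate is given. Section 3.3.2 has a rule of at least 56 meetings per discipline, which is 2 × 28, without a split by phase. Attendance bias is possible but cannot be sized.

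**The stakes are modest.** The primary endpoint is qualitative, and speaking time is one of several team-function measures.

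**Conclusion.** The protocol's speaking-time model omits a source of dependence that the protocol itself names and handles elsewhere. Its stated 5% level holds only if essentially the same clinicians are observed in both phases.

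Where clinicians differ wholly or partly, which sections 3.1.3, 3.1.5 and 3.3.2 make plausible, the false-positive rate is about 7–19% in the partial-overlap case and 11–32% in the no-overlap case. These figures rest on assumed correlations of 0.1 to 0.5, 8 and 3 clinicians, and 23 meetings per phase; the documents give neither the correlation nor the overlap.

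The supportable statement is that the standard error can be too small, not that it must be. The point concerns a tested secondary outcome and should be corrected before the analysis. It does not threaten the study's primary aim.

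**What to change.** 1. Make the main speaking-time model unconditional and fit it with one row per clinician per meeting. Include phase, meeting length, the number of clinicians of that discipline present, and a clinician random intercept with a small-sample correction to the degrees of freedom. Section 5.2.1 already measures each member's speaking time and section 5.1.1 provides for speaker attribution, so no new data are needed.
2. Do not simply copy the clinician fixed effects from the skill model. They use only clinicians seen in both phases, and with no overlap the phase effect cannot be estimated.
3. Reconcile sections 3.1.3 and 4.3 on who is recorded before training. Report each discipline's attendance, and the number of clinicians common to both phases, by phase.
4. Align protocol sections 5.1.1, 5.2.1, 6.2, 6.3.2 and 6.4 with the SAP on outcome (minutes or words), groups (disciplines, or physicians and parents) and model. State the difference, SD and correlation behind the figure of 3 pairs.

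The cost is a wording change and a slightly larger model. Confidence intervals will be wider in most cases and may be narrower if the same clinicians attend evenly. If there is little overlap, the model gives honest uncertainty but cannot separate training from differences between volunteers and other clinicians. The report should say so.
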